Advancements in cellular therapies for hematologic malignancies (HM)—notably allogeneic stem cell transplantation (allo-SCT) and chimeric antigen receptor T-cell (CAR-T) therapies—have significantly improved clinical outcomes and survival for patients with otherwise limited treatment options [1–3]. Allo-SCT remains a curative approach for many malignant hematologic conditions through graft-versus-leukemia effects but is associated with considerable short- and long-term morbidity, including graft-versus-host disease (GVHD), infectious complications, and delayed quality of life recovery [4–6]. CAR-T therapy, by contrast, has revolutionized the management of relapsed or refractory B-cell malignancies, offering durable responses in heavily pretreated patients. However, CAR-T is characterized by unique acute toxicities such as cytokine release syndrome (CRS) and immune effector cell-associated neurotoxicity syndrome (ICANS), which often occur during the index hospitalization and substantially affect symptom burden [7–9].

Despite the transformative impact of these therapies, there remains a paucity of real-world data describing short-term patient-reported outcomes (PROs) during the acute inpatient phase of treatment. While long-term quality of life trajectories have been studied in both allo-SCT and CAR-T cohorts [10–12], less is known about patients' immediate experiences throughout hospitalization, when symptom burden is highest and when clinical and supportive care decisions are most critical. Importantly, a recent prospective longitudinal study directly compared PROs across CAR-T, autologous SCT, and allo-SCT recipients. This study demonstrated that although all groups experienced a decline in quality of life with a nadir around week 2, CAR-T recipients had a significantly less severe decline and a faster recovery compared to allo-SCT patients, who experienced the greatest symptom burden and slowest recovery [13]. These findings underscore the need for further prospective, real-world research to better characterize short-term PRO trajectories in these populations and to confirm these observations in diverse clinical settings. Understanding these short-term experiences has implications for optimizing symptom management, resource utilization, discharge readiness, and early survivorship care [14,15].

The Hematological Malignancy Patient-Reported Outcome (HM-PRO) is a validated instrument specifically developed to assess health-related quality of life (HRQoL) and symptom burden in patients with HM [16–20]. It consists of two parts: Part A evaluates the impact of disease and treatment on HRQoL, and Part B assesses the severity of symptoms. HM-PRO has undergone rigorous psychometric validation, demonstrating strong content validity, construct validity, reliability, and sensitivity to change across a broad spectrum of hematologic malignancies [16–18]. Its disease-specific design makes it particularly suitable for capturing the dynamic and treatment-specific symptom profiles observed in allo-SCT and CAR-T recipients.

Given the distinct toxicity and recovery profiles of allo-SCT and CAR-T therapy, a prospective observational study is warranted to compare short-term PRO trajectories between these two patient groups during the inpatient treatment course. Observational methodology is appropriate, as treatment allocation is determined by clinical indication rather than

randomization, and such a design enables the capture of real-world patient experiences in a non-interventional setting [21,22]. By employing the HM-PRO to collect PRO data at baseline, throughout hospitalization, and at discharge, this study will generate high-resolution, real-world evidence on patient experiences that are currently underrepresented in the literature. These findings will help inform supportive care strategies, improve patient-centered decision-making, and contribute to comparative effectiveness research in advanced cellular therapies.

2. Study Objectives

Primary Objective:

- To assess and compare short-term patient-reported outcomes [PROs (symptom burden and QoL impact)] between patients receiving allo-SCT and CAR-T therapy using the HM PRO from admission to hospital discharge.

Secondary Objectives:

- To describe PRO trajectories during hospitalization.
- To assess differences in PROs based on:
 - Treatment modality (allo-SCT vs CAR-T)
 - Disease type (e.g., AML, lymphoma, myeloma)
 - Disease status (remission vs progression)
 - Treatment line (first-line vs multiple lines)
- To validate the use of the HM-PRO in the context of inpatient care for advanced therapies.

3. Study Design

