3.1. Overview

Prospective, multicenter, observational cohort study comparing short-term PROs measured with the HM-PRO between two exposure groups: patients undergoing allogeneic stem cell transplantation (allo-SCT) and patients receiving CAR-T cell therapy. Patients will be enrolled at hospital admission for the index inpatient procedure and followed through the inpatient stay (admission → discharge). The study is non-randomized and designed to describe trajectories of symptoms and HRQoL and to estimate the between-group difference in deterioration of HM-PRO scores (primary estimand: mean difference in change score, CAR-T vs allo-SCT).

3.2 Setting:

Two tertiary care hospitals in Rome, Italy, with active allo-SCT and CAR-T in patient programs; multicenter to improve generalizability.

3.2 Duration:

1 year enrollment, participation from hospital admission to discharge (maximum 3 months).

4. Population

One hundred and sixty-two adults (≥ 18 years) with a hematologic malignancy admitted for either (a) allo-SCT (N=81) or (b) CAR-T cell therapy (N=81).

4.1 Inclusion Criteria:

- Age ≥ 18 years
- Diagnosed with a hematologic malignancy (e.g., leukemia, lymphoma, multiple myeloma)
- Undergoing either allogeneic SCT or CAR-T therapy
- Able and willing to provide written informed consent
- Sufficient Italian proficiency to complete the HM-PRO
- Signed informed consent

4.2 Exclusion Criteria:

- Cognitive or physical impairments that preclude the ability to complete questionnaires
- Estimated life expectancy < 7 days at the time of admission

5. Assessment Schedule

Patient-reported outcomes will be collected using the HM-PRO instrument at the following time points:

- T1: Hospital admission
- T2: Day of infusion (CAR-T or stem cell infusion)
- T3: Day 3 post-infusion
- T4: Day 10 post-infusion
- T5: Day of hospital discharge

6. Collected Variables

Demographics:

- Age, Gender, Education level, occupation, civil status

Clinical Variables:

- Comorbidities, Disease type, Disease status (remission/progression), Line of treatment

Laboratory:

- Full blood counts

Treatment:

- CAR-T or allo-SCT treatment details, including conditioning regimen and product specifics

Adverse Events:

- Documented using CTCAE criteria, including:
 - Mucositis, Infections, GvHD, CRS, ICANS

Patient-Reported Outcomes:

- HM-PRO (Impact Scale, Symptoms Scale)

7. Endpoints

Primary Endpoint:

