- Difference in HM-PRO total and domain scores between allo-SCT and CAR-T groups at each time point (T1–T5)

Secondary Endpoints:

- Change in HM-PRO scores over time within each group
- Comparison of PROs by disease status and treatment line
- Frequency and severity of adverse events and correlation with PRO data

8. Statistical Analysis

- All analyses will be performed using two-sided tests with a nominal significance level of $\alpha = 0.05$ unless otherwise stated. Estimates will be reported with 95% confidence intervals.

Primary analysis population include all enrolled participants with at least one post-baseline HM-PRO assessment (intention-to-observe principle).

- Baseline demographic and clinical variables will be summarized by treatment group (allo-SCT vs CAR-T).

- **Continuous variables:** mean (SD) and median (IQR) as appropriate.
- **Categorical variables:** counts and percentages.
- Between-group baseline comparisons will be descriptive (t-tests/Wilcoxon tests or chi-square/Fisher exact tests) to display balance; inferential testing of baseline covariates is not the primary focus. A baseline table will be produced.

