- Multiple secondary endpoints and subgroup tests are planned; these will be described as exploratory. Where formal control of family-wise error is desired for predefined secondary endpoints, procedures (e.g., Holm or Benjamini-Hochberg false discovery rate) will be specified in the SAP.

Additional analyses

- **Proportion with clinically meaningful deterioration:** compute proportion of participants with ≥ 6 -point worsening from baseline to discharge and compare groups using chi-square tests and logistic regression adjusted for covariates; report risk differences and adjusted odds ratios with 95% CIs.
- **Sensitivity for clustering:** if substantial between-site heterogeneity is present, use mixed models with random site intercepts or a generalized estimating equations (GEE) approach with robust SEs clustered by site.
- **Exploratory trajectories:** use latent class growth modelling or clustering of longitudinal profiles if warranted to identify common PRO trajectory phenotypes (reported descriptively).

Reporting

- All results will be reported according to STROBE guidance for observational studies and following best practices for PRO reporting (including instrument scoring details, number of missing items, and sensitivity analyses). Statistical code and de-identified

analytic datasets will be archived as per institutional policies and will be made available on reasonable request, consistent with GDPR and ethics approvals.

8.2. Sample Size:

The primary objective was to detect a between-group difference in HM-PRO between groups based on the difference in HM-PRO total score of $\Delta = 6$ points (the established Minimal Important Difference). Assuming a two-sided $\alpha = 0.05$ and 80% power, the required sample size per group was calculated using the two-sample t-test formula:

$$n = (2(z_{(1-\alpha/2)} + z_{(1-\beta)})^2 \sigma^2) / \Delta^2$$

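### The primary objective covers two HM-PRO outcomes, but the plan sizes one undefined total score and sets no order or error control between the scores that could carry the primary claim

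*Protocol*

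**What the plan says.** Section 2 states the primary objective as "To assess and compare short-term patient-reported outcomes [PROs (symptom burden and QoL impact)] between patients receiving allo-SCT and CAR-T therapy", so two constructs are named. The background text before Section 2 describes the instrument: "It consists of two parts: Part A evaluates the impact of disease and treatment on HRQoL, and Part B assesses the severity of symptoms". Section 6 lists the data collected as "HM-PRO (Impact Scale, Symptoms Scale".

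Section 3.1 gives the "primary estimand: mean difference in change score, CAR-T vs allo-SCT" and does not say which score changes. Section 7 gives the primary endpoint as "Difference in HM-PRO total and domain scores between allo-SCT and CAR-T groups at each time point (T1–T5". Section 8.1 then treats the primary endpoint as change from baseline to discharge and analyses it by ANCOVA on the discharge HM-PRO, again without naming a scale. The additional analysis of worsening by at least 6 points also names none.

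Section 8.2 sizes the study "based on the difference in HM-PRO total score of" 6 points.

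On error control, Section 8 says "All analyses will be performed using two-sided tests with a nominal significance level" of 0.05, unless otherwise stated. Section 8.1, under multiplicity, says "Multiple secondary endpoints and subgroup tests are planned; these will be described as exploratory". What it leaves to the SAP is control for predefined secondary endpoints.

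**The concern.** A reader cannot tell which number answers the primary question. The candidates are the Part A score, the Part B score, a score built from both, and the domain scores. Fixing one time point and one model would not settle this, because the choice of scale would still be open.

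The two parts can disagree. CAR-T and allo-SCT might differ on symptoms but not on impact, and the plan has no rule for what the study would then conclude. If the scale is chosen after the data are seen, the nominal 0.05 no longer describes the primary claim. The 80% power was computed for one score and does not automatically carry over to an objective that covers two.

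**Working it through.** **1. Reproduce the plan's sample size.** Inputs from Section 8.2: difference 6, two-sided alpha 0.05, power 80%, SD 12 or 15, baseline correlation r = 0.5 for the ANCOVA case, 10% inflation. Formula: n = 2(1.960 + 0.842)² σ² / Δ².

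| Case | σ² | n per group | Stated |
|---|---|---|---|
| SD 12 | 144 | 62.79 | 63 |
| SD 15 | 225 | 98.11 | 98 |
| SD 15, r = 0.5 | 225 × 0.75 = 168.75 | 73.58 | 74 |

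Inflation: 73.58 × 1.1 = 80.9, which gives the stated 81. The arithmetic reproduces to rounding. At 74 per group, power is 80.2% by the normal formula and 79.7% by noncentral t. All of this is for one test of one score.

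**2. Which score each place uses.**

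| Place | Score named |
|---|---|
| Section 2, primary objective | Symptom burden and QoL impact |
| Section 3.1, estimand | None (change score) |
| Section 6, data collected | Impact Scale and Symptoms Scale |
| Section 7, primary endpoint | Total and domain scores, T1–T5 |
| Section 8.1, ANCOVA | None (discharge HM-PRO) |
| Section 8.1, worsening by 6 points or more | None |
| Section 8.2, sample size | Total score, not defined |

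**3. False-positive rate under each possible rule.** The protocol states no rule, so each line is conditional.

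- *One defined score alone is primary:* 5%.
- *Both scales must be significant:* at most 5%, because a false claim needs at least one true null to be rejected at 0.05.
- *Either scale suffices, one test per scale:* 1 − P(|Z₁| ≤ 1.96 and |Z₂| ≤ 1.96). With independent scales this is 1 − 0.95² = 9.75%. For correlated scales it comes from the bivariate normal. The between-scale correlation is an assumption, since the protocol gives none.

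| Correlation | 0 | 0.3 | 0.5 | 0.7 | 0.8 | 0.9 |
|---|---|---|---|---|---|---|
| Rate | 9.75% | 9.5% | 9.1% | 8.35% | 7.8% | 7.0% |

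- *Either scale at several time points:* with independence as an upper figure, 1 − 0.95⁸ = 33.7% for two scales at four post-baseline times, and 1 − 0.95¹⁰ = 40.1% at all five. Repeated scores are correlated, so the true values would be lower.

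**4. Cost of the two usual remedies.** Splitting alpha at 0.025 per scale (SD 15, r = 0.5, and 6 points assumed on each scale) gives n = 89.1, so 90 per group before dropout against 74. Allowing for dropout gives 90 / 0.9 = 100, against the planned 81. With 74 evaluable per group, power per scale at 0.025 would be 71.5%. A fixed order holds the family-wise rate at 0.05 and leaves 74 and 81 unchanged for the first-ranked score.

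**The case against.** The strongest reply is that Section 8.2 already picks one score. If the total score is the only primary outcome, the error rate is 5% and nothing is inflated. The study is also a non-randomized cohort meant to describe and estimate, with a nominal alpha and confidence intervals, and scoring follows a manual that the protocol cites. The word total may simply mean the total of one part.

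Part of this stands. It rules out three stronger inferences that a reader might draw.

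- *That the primary claim has a false-positive rate of about 9%.* This needs success on either scale, one test per scale and a correlation near 0.5. The protocol states none of these.
- *That power for the objective is really about 67% to 72%* (both scales significant, correlation 0.3 to 0.7), *or 33% to 41%* (scales averaged, 6 points on one scale only). These figures assume a both-must-succeed rule or an averaged score, and the plan states neither. The first rule also cannot be combined with the 9% figure, because it keeps the error at or below 5%.
- *That Parts A and B must not be summed.* That depends on the scoring manual, which is not in the documents. The protocol describes one instrument in two parts.

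The reply does not remove the core point. The sized score is undefined, and Sections 2 and 7 name more than that one score as primary. Section 8.2 speaks of detecting a difference at two-sided 0.05 with 80% power, and Section 8.1 asks for p-values on the primary contrasts, so naming the deciding score is a fair request. Nor is the matter deferred to the SAP, since the multiplicity text defers only control for secondary endpoints.

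**Conclusion.** The point holds as an unresolved choice of primary score; it does not establish an error rate for the plan. The objective covers two outcomes, the endpoint lists total and domain scores, one undefined total score is sized, and nothing orders or controls the tests within the primary family. The stated 0.05 and 80% power are therefore valid for one score only.

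The size depends on the rule eventually applied: 5% with a single defined score, at most 5% if both scales must succeed, and 7.0% to 9.75% if either suffices with one test each. The last range assumes a between-scale correlation of 0.9 down to 0. The rate is higher if all domains and time points count as primary. The sample-size arithmetic itself is not in dispute. This should be corrected before data are examined.

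**What to change.** In Sections 3.1, 7, 8.1 and 8.2:

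- Define the HM-PRO total score according to the scoring manual, and name that score as the sole primary outcome for the change-to-discharge contrast.
- State that the 6-point difference and the 80% power refer to that score.
- Test the other scale at two-sided 0.05 only if the first is significant, or label it secondary. Label domain scores exploratory.
- State which score the 6-point worsening rate uses. Apply 6 points to another scale only if the sponsor can support that threshold for it, because the protocol gives it for the total score alone.

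The cost is wording in the protocol and SAP, with no extra patients and no alpha lost on the first-ranked score. The downside is that the second scale supports a confirmatory claim only after the first succeeds, and the stated power covers the first-ranked score only.

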3.1. Overview

Prospective, multicenter, observational cohort study comparing short-term PROs measured with the HM-PRO between two exposure groups: patients undergoing allogeneic stem cell transplantation (allo-SCT) and patients receiving CAR-T cell therapy. Patients will be enrolled at hospital admission for the index inpatient procedure and followed through the inpatient stay (admission → discharge). The study is non-randomized and designed to describe trajectories of symptoms and HRQoL and to estimate the between-group difference in deterioration of HM-PRO scores (primary estimand: mean difference in change score, CAR-T vs allo-SCT).

3.2 Setting:

Two tertiary care hospitals in Rome, Italy, with active allo-SCT and CAR-T in patient programs; multicenter to improve generalizability.

3.2 Duration:

1 year enrollment, participation from hospital admission to discharge (maximum 3 months).

4. Population

One hundred and sixty-two adults (≥ 18 years) with a hematologic malignancy admitted for either (a) allo-SCT (N=81) or (b) CAR-T cell therapy (N=81).

4.1 Inclusion Criteria:

- Age ≥ 18 years
- Diagnosed with a hematologic malignancy (e.g., leukemia, lymphoma, multiple myeloma)
- Undergoing either allogeneic SCT or CAR-T therapy
- Able and willing to provide written informed consent
- Sufficient Italian proficiency to complete the HM-PRO
- Signed informed consent

4.2 Exclusion Criteria:

- Cognitive or physical impairments that preclude the ability to complete questionnaires
- Estimated life expectancy < 7 days at the time of admission

5. Assessment Schedule

Patient-reported outcomes will be collected using the HM-PRO instrument at the following time points:

- T1: Hospital admission
- T2: Day of infusion (CAR-T or stem cell infusion)
- T3: Day 3 post-infusion
- T4: Day 10 post-infusion
- T5: Day of hospital discharge

6. Collected Variables

Demographics:

- Age, Gender, Education level, occupation, civil status

Clinical Variables:

- Comorbidities, Disease type, Disease status (remission/progression), Line of treatment

Laboratory:

- Full blood counts

Treatment:

- CAR-T or allo-SCT treatment details, including conditioning regimen and product specifics

Adverse Events:

- Documented using CTCAE criteria, including:
 - Mucositis, Infections, GvHD, CRS, ICANS

Patient-Reported Outcomes:

- HM-PRO (Impact Scale, Symptoms Scale)

7. Endpoints

Primary Endpoint:

- Difference in HM-PRO total and domain scores between allo-SCT and CAR-T groups at each time point (T1–T5)

Secondary Endpoints:

- Change in HM-PRO scores over time within each group
- Comparison of PROs by disease status and treatment line
- Frequency and severity of adverse events and correlation with PRO data

8. Statistical Analysis

- All analyses will be performed using two-sided tests with a nominal significance level of $\alpha = 0.05$ unless otherwise stated. Estimates will be reported with 95% confidence intervals.

Primary analysis population include all enrolled participants with at least one post-baseline HM-PRO assessment (intention-to-observe principle).

- Baseline demographic and clinical variables will be summarized by treatment group (allo-SCT vs CAR-T).

- **Continuous variables:** mean (SD) and median (IQR) as appropriate.
- **Categorical variables:** counts and percentages.
- Between-group baseline comparisons will be descriptive (t-tests/Wilcoxon tests or chi-square/Fisher exact tests) to display balance; inferential testing of baseline covariates is not the primary focus. A baseline table will be produced.

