8.1 Primary longitudinal analysis (HM-PRO)

- **Primary modelling approach:** linear mixed-effects models (LMM) for repeated measures of HM-PRO scores to evaluate within-hospital trajectories and between-group differences. The base model will include:
 - Fixed effects for **timepoint (categorical: T1, T2, T3, T4, T5), treatment group**, and the **group × time** interaction (to test for differential trajectories).
 - A random intercept for participant to account for within-subject correlation; random slope for time will be considered if supported by data and model fit.
 - Prespecified covariates: baseline HM-PRO score (if modelling discharge score via ANCOVA alternatively), age, sex, disease type, disease status, line of therapy, major comorbidity index, and site (as fixed effect or as random effect in a hierarchical model).

- Parameter of interest: the group \times time interaction contrasts (e.g., difference in mean change from baseline to discharge between groups). Report estimated marginal means (least-squares means), differences, 95% CIs and p-values.
- **Model diagnostics:** check residuals for normality and heteroscedasticity, influence diagnostics, and perform sensitivity analyses using robust standard errors if necessary. If severe non-normality persists, consider transformation or a generalized linear mixed model (GLMM) or rank-based mixed model.

Repeated measures ANOVA

- As a supportive analysis (or when assumptions are met and complete data are available), repeated-measures ANOVA (with Greenhouse-Geisser correction if sphericity violated) may be used to summarize overall time and group effects. Primary inference will rely on mixed models which better accommodate missingness and unequal intervals.

Between-group comparisons & ANCOVA

- For the primary endpoint specified as change from baseline to discharge, an **ANCOVA** model will be used (discharge HM-PRO as outcome, baseline HM-PRO as covariate, plus the same prespecified covariates). This produces an adjusted estimate of the between-group difference in mean change.
- Unadjusted two-sample t-tests (or nonparametric Wilcoxon tests) will be presented for transparency.

Subgroup analyses

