Because the SD of HM-PRO change in our population is uncertain, we present results for a range of plausible SDs: for SD = 12 the required sample size is 63 per group (80% power); for SD = 15 it is 98 per group. If the primary analysis adjusts for baseline HM-PRO using ANCOVA and the correlation between baseline and outcome is r , the residual variance is approximately $\sigma^2 (1-r^2)$ and the required sample size is reduced accordingly (for example, with SD = 15 and $r=0.5$, $n \approx 74$ per group). We inflated the calculated sample size by 10% to allow for anticipated loss to follow-up (final target n per group = 81). All sample-size calculations were performed in R using power.t.test.

9. Methods

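### Section 7's primary endpoint (all HM-PRO scores at T1 to T5) contradicts the change contrast in 3.1 and 8.1 and does not match the single difference sized in 8.2; Section 8.1 also assigns the primary result to two models

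*Protocol*

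**What the plan says.** The protocol describes its primary comparison in several places, and the descriptions differ.

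- **Section 7**, the only entry under the primary endpoint: "Difference in HM-PRO total and domain scores between allo-SCT and CAR-T groups at each time point (T1–T5". These are score levels, for several scores, at five visits. The only change endpoint in Section 7 is secondary and concerns change within each group.
- **Section 3.1**: "primary estimand: mean difference in change score, CAR-T vs allo-SCT". Neither the score nor the time point is named.
- **Section 8.1, mixed model**: the parameter of interest is the set of group-by-time contrasts, with "difference in mean change from baseline to discharge between groups" offered only as an example.
- **Section 8.1, ANCOVA paragraph**: "For the primary endpoint specified as change from baseline to discharge", ANCOVA will be used. Section 7 does not list this endpoint.
- **Section 8.2**: the study is sized for a "between-group difference in HM-PRO between groups based on the difference in HM-PRO total score of" 6 points. Change is not stated there. It is implied by the next step ("Because the SD of HM-PRO change in our population is uncertain") and by the ANCOVA variance reduction.

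On the model, Section 8.1 labels linear mixed models the primary approach and, when contrasting them with repeated-measures ANOVA, adds: "Primary inference will rely on mixed models which better accommodate missingness and unequal intervals". The baseline score appears in the covariate list only for the case where ANCOVA is used instead. The multiplicity paragraph of Section 8 deals with secondary endpoints and subgroups and does not mention several primary comparisons.

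**The concern.** A difference in score level at a visit and a difference in change from baseline are separate quantities, and here the groups may differ at the start. Section 3.1 says so in effect: "The study is non-randomized and designed to describe trajectories of symptoms and HRQoL". Section 9.3 labels T1 as baseline. A T1 difference therefore describes who received which treatment, yet Section 7 includes it in the primary endpoint. Section 8 treats the other baseline comparisons as descriptive.

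Two analysts could each follow the protocol and report different primary results. One would report total or domain scores at any of five visits under Section 7. The other would report the T1-to-T5 change under the ANCOVA paragraph of 8.1, and could take it from either of two models that do not have the same power. The sample size supports only one of these readings.

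**Working it through.** **Inputs, all from Section 8.2:** difference 6 points; two-sided 0.05; 80% power; SD 12 or 15; baseline–outcome correlation r = 0.5; 10% inflation; final target 81 per group. Evaluable per group: 81 × 0.9 = 72.9, taken as 73.

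**Step 1. Reproduce the plan's figures.** n per group = 2 × (1.960 + 0.842)² × SD² / 6².

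- SD 12: 62.8, so 63. Stated: 63.
- SD 15: 98.1. Stated: 98 (strict rounding up gives 99, which is immaterial).
- SD 15 with r = 0.5: residual SD = 15 × √(1 − 0.25) = 12.99, n = 73.6, so 74. Stated: 74.

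**Step 2. Find where 81 comes from.**

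- ANCOVA case: 73.6 × 1.1 = 80.96, so 81 (from the rounded 74, 81.4).
- Unadjusted, SD 12: 63 × 1.1 = 69.3.
- Unadjusted, SD 15: 98 × 1.1 = 107.8.

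Only the ANCOVA case gives 81. It is one comparison on one score.

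**Step 3. Power for the T1-to-T5 contrast under each model.** Normal approximation: power = Φ(6 / (SD × √(2/73)) − 1.960), with √(2/73) = 0.1655.

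| Analysis | SD used | 6 / SE | Power |
|---|---|---|---|
| ANCOVA, SD 15, r = 0.5 | 12.99 | 2.79 | 0.797 |
| ANCOVA, SD 12, r = 0.5 | 10.39 | 3.49 | 0.937 |
| Mixed model, T1 as outcome, no baseline covariate, SD 15 | 15 | 2.42 | 0.676 |
| Same mixed model, SD 12 | 12 | 3.02 | 0.856 |

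The mixed-model rows take 8.2's SD as the SD of change, as 8.2 describes it. The ANCOVA formula needs the SD of the score. The two agree at r = 0.5: with equal variances at T1 and T5, the variance of change is 2 × σ² × (1 − 0.5) = σ². No row credits any gain from the other prespecified covariates.

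**The case against.** The strongest reply is that Section 7 may be what the sponsor intends. The study is observational, reports estimates with 95% intervals, and has a primary objective (Section 2) that covers symptom burden and quality of life over the whole stay. That is broader than one total-score contrast and nearer to Section 7. The background also points to a nadir around week 2, which makes day 10 of interest. This much stands: the documents do not show which description was meant, so the choice belongs to the sponsor. It does not remove the conflict. Section 8 sets two-sided tests at 0.05, 8.1 asks for p-values, and 8.2 powers one difference. Nor is this detail left to the SAP, because the protocol itself names two incompatible primary endpoints.

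Several stronger readings are tempting, and the documents do not support them.

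- **That the protocol is silent on the primary model.** It is not: 8.1 names the mixed model. The defect is that it then assigns the primary endpoint to ANCOVA.
- **That every section except 7 clearly specifies baseline-to-discharge change.** Section 8.2 only implies change, and the mixed-model text gives that contrast as an example.
- **That the planned analyses would present a T1 difference as a treatment effect.** The interaction contrasts subtract T1 and ANCOVA conditions on it. The fault lies in Section 7's wording.
- **That the false-positive rate is inflated by a known amount.** Any such figure needs a rule that one significant result suffices and a number of domain scores. The protocol states neither.
- **That a mixed model necessarily loses power.** The loss belongs to the form written in 8.1. A mixed model of post-baseline scores with baseline as a covariate would keep the gain behind 74 per group.
- **That the sample size is miscalculated.** Its figures reproduce.

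**Conclusion.** The point holds as an unreconciled contradiction that must be resolved before analysis. Section 7's endpoint is incompatible with the estimand in 3.1 and the ANCOVA paragraph in 8.1, and it is not what 8.2 sizes. Section 8.1 also conflicts with itself on the model. At SD 15 that second conflict is worth about 12 percentage points of power (80% against 68%). At SD 12 it is about 8 points (94% against 86%), and both models exceed 80%. These figures assume 73 evaluable per group, r = 0.5, equal variances at T1 and T5, and a true difference of 6 points. The contradiction itself rests on no numerical assumption.

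**What to change.** Name one primary score, one contrast and one model, and use the same wording in Sections 3.1, 7, 8.1 and 8.2.

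- **Option that fits the present size:** T1-to-T5 change in the HM-PRO total score, stating which score that is, estimated by ANCOVA with the mixed model as supportive. This matches the ANCOVA paragraph of 8.1 and leaves 81 per group unchanged, provided the 6 points and the SD apply to the named score.
- **If the sponsor prefers another contrast (day 10, for example) or the mixed model:** restate 8.2 for that choice. For a mixed-model change contrast without a baseline covariate, 8.2's unadjusted 63 (SD 12) or 98 (SD 15) apply before inflation. With post-baseline scores as outcomes and baseline as a covariate, the reasoning behind 74 carries over.
- **In either case:** make the remaining time points and the domain scores secondary under the multiplicity approach already described in Section 8, and report T1 descriptively.

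Under the first option the cost is wording only. The downside is that the time points not chosen are no longer primary, though the mixed model still estimates them with 95% confidence intervals.
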